Title

Addition of pre-wound closure povidone iodine wash versus direct wound closure effect on surgical site infections: A randomized controlled trial

NCT Number: Not Yet assigned

Date: 11th of September, 2021

Background

Surgical site infections are post-operative infections of the incision or organ or space that was included in the surgical field [1]. Incisional surgical site infections (SSIs) are a growing healthcare challenge [2]. Currently, up to 10% of surgical procedures may be complicated by an SSI [3]. Not only do SSIs lead to worse patient outcomes, but they also account for a large proportion of healthcare expenditure [4-6]. In the United Kingdom alone, SSIs are estimated to cost the National Health Service 1 billion pounds annually [7]. The problem is further compounded in low- and middle-income countries (LMICs) where the prevalence of antibiotic-resistant infections is increasing, and national healthcare budgets are strained [8]. In fact, SSIs are estimated to account for additional costs of up to \$30,000 in LMICs [9].

The global crisis of drug-resistant bacteria has further highlighted the need for more effective perioperative preventive strategies to minimize healthcare-associated resistant infections [10,11]. Optimal surgical antisepsis is critical in reducing the incidence of SSIs, and therefore in reducing the use of post-operative antibiotics [12,13]. Recently, there has been a renewed interest in using povidone-iodine (PVI) intraoperative wound irrigation to achieve this goal. The choice of PVI is especially suitable for LMICs where the availability of chlorhexidine preparations may be limited by scarce resources [14].

A possible adjunctive role of pre-wound closure PVI irrigation in reducing incisional SSIs is still unclear [15,16]. A meta-analysis by López-Cano et al. analyzed data of 7,601 patients and found a reduction in overall SSI rate. However, the heterogeneity and uncertain quality of most studies limited the synthesis of conclusive evidence [17]. The possible benefits of irrigating the surface of an open incision include local antimicrobial effect, physical removal of debris and dilution of contamination. Recent guidelines have all emphasized the lack of sufficient evidence on intraoperative use of PVI [18-21].

We aim to conduct a randomized controlled trial in Ain Shams University Hospitals to compare the effect of adding PVI wash prior to skin closure to direct wound closure on reducing the rates of SSIs.

Study Objective

To assess the efficacy of povidone-iodine wash before wound closure in preventing surgical site infections.

Trial Design

Superiority, parallel group randomized controlled trial, allocation 1:1

Methods

Study Setting

Operative theatres at Ain Shams University Hospitals

Inclusion Criteria

- Adult patients (≥ 18 years old)
- Open and minimally invasive surgeries
- Emergency (any unplanned admission) and elective (planned admission) surgical procedures
- Clean, Clean-Contaminated, Contaminated, Dirty wounds [22], (See appendix 1)
- Inclusion surgery list according to Current Procedural Terminology (CPT) National Healthcare Safety Network (NHSN) operative procedure code mapping [23] , List of included surgical procedures (See appendix 2)

Exclusion Criteria

- Povidone-iodine allergy
- Surgeries for infected wounds.
- Exclusion surgery list according to Current Procedural Terminology (CPT) National Healthcare Safety Network (NHSN) operative procedure code mapping, [23] List of excluded surgical procedures, (See appendix 3)

Intervention

- 10% povidone iodine wound wash before wound closure versus direct wound closure.
- Antibiotic prophylaxis will be administered according to local protocols.
- Wound dressing type and frequency will not differ between both groups.
- Diagnosed SSIs will be managed according to local antibiograms and management guidelines.

Outcomes

- Primary: Incidence of superficial and deep surgical site infection (SSI) within 30 days postoperatively
- Secondary:
 1. Post-operative morbidity and mortality by (Clavien-Dindo classification system) [24], (See appendix 4)
 2. Length of hospital stay
 3. Readmission and Reoperations related to surgical site infection
 4. Infectious complications (Sepsis, septic shock, multiple-organ dysfunction syndrome, wound dehiscence) [25-28]
 5. Microbiology culture and sensitivity results
 6. Local adverse events for povidone-iodine application (Local irritation, poor wound healing)
 7. Cost-analysis

Participant Timeline

Recruitment will start from day (18/09/2021) till sample size is reached.

Patients will be introduced to and asked to participate in the trial when they arrive to the surgical ward or emergency department by the surgical resident. They will not be subjected to any additional steps other than the standard hospital protocols as our trial begins in the operating room where patients will be randomly allocated into 2 groups: the control group (direct wound closure) and the intervention group (PVI wound wash before closure).

After the operation, patients will be monitored and observed at the hospital by the staff until discharge and will be given a specialized follow-up card. Following discharge, follow-up will be in the form of fixed outpatient clinic visit after the first week postoperatively and continue with phone calls made at regular 1-week intervals inquiring about symptoms and signs of SSI based on a questionnaire guided by the CDC definitions [27]. If a patient displays ≥ 1 symptom listed in the CDC checklist (See appendix 5), he/she will be invited to follow-up in our outpatient clinic and will be identified by their card. This will allow the physician to fill out the data collection form in their files and obtain a picture for documentation purposes. Follow-up will continue for a period of 30 days.

Sample Size

Using PASSII program for sample size calculation and assuming SSI incidence of 10% in control group and 5% in intervention group, setting **power** at 80% and **α -error** at 0.05, sample size of 345 patient for each group will be needed. We plan to enroll an additional 10% of the calculated sample size for each group in anticipation of a loss to follow-up rate of 10%. The total sample size will be **760 patients**.

Assignment of Interventions

Sequence Generation

A statistician not directly involved in the study or analysis will prepare a computer-generated randomization sequence. No blocking will be used. The sequence will be provided to the trialists in the form of serially numbered opaque envelopes containing details of either the intervention or the control and a random identifier.

Enrolment and Allocation Concealment

The patients will be enrolled by the resident doctors and given a study ID number.

The allocation sequence will be made available to the OR head nurse in the form of sealed envelopes. The head nurse will provide the surgeons with closed opaque envelopes which will be opened by the nurse directly before wound closure. The head nurse will ensure that the envelopes are opened at wound closure and not before it. After the intervention/control is carried out, the random identifier will be noted down in the patient's operative data collection form. Following that, the nurse will tear the envelope and its contents.

Blinding

The patients and outcome assessors will be blinded. The details of which intervention was used will not be recorded in the regular patient records. The surgeons will be blinded till directly before wound closure, however, because of the nature of intervention, complete blinding of the surgeons would be impossible.

Data Collection Methods

Preoperative data collection will aim to collect baseline data about the recruited patients: patient identifiers, age, BMI, comorbidities including hypertension, diabetes, CKD, chronic liver disease, chronic heart failure, as well as any documented medication use and ASA score; through a standardized data collection form. All patients will be monitored by the doctors who will be responsible for filling their follow-up data till 30 days postoperatively (See appendix 6 for data collection forms).

Teams of four (surgeons or medical students) will be recruited to collect data from included surgical departments, each team collecting information over a two-week interval from all patients undergoing included surgical procedures in the department. Teams will then follow up with patients recruited in this allowed interval over the 30-day follow-up period, according to the methods described above.

We will obtain written informed consent from participants before surgery explaining the study procedures and the follow-up plans. All those who volunteer will be followed up in our clinics and provided carefree-of-cost.

Data Management

Package: R (latest available version)

Methods: Descriptive statistics will be presented as mean \pm SD for quantitative data. If the data is severely skewed/not normally distributed, median and IQR will be used. N & percentile will be used for qualitative data. Relevant statistical tests will be reported when applicable.

Statistical Methods

Suitable statistical tests will be used for data analysis.

The study participants will be divided into 4 groups (Clean, Clean-contaminate, Contaminated, Dirty).

Each group will be stratified and analyzed separately.

Subgroup analyses will also be performed according to the type of surgical access (open versus minimally invasive), and the presence or absence of Diabetes.

The need for additional subgroup analyses will be determined at the time of completion of data collection.

Both per-protocol and intention to treat analyses will be used and their findings will be reported.

Monitoring

The study will not employ a data monitoring committee (DMC) as the trial is conducted on an adult population with no perceived risk to either arm of the trial.

Interim analysis will be done on reaching 50% of the total sample size by an independent statistician blinded for the intervention allocation. The unblinded data will be reported to the Ain Shams Surgical Research Group. The primary purpose of this analysis would be to determine if the study should be prematurely terminated in the case of patient harm. The final decision on the matter will reside with the Ain Shams Surgical Research Group and the study's principal investigators.

In our study an adverse event will be defined as any medical occurrence in a subject with a probable causal relation to the intervention.

Adverse events will be collected after the subject has provided consent and enrolled in the study.

The known as well as novel adverse effects of the study intervention (povidone iodine) will be investigated and recorded until the period of patient follow up is completed.

Ethics and Dissemination

Ethical Approval

This protocol, the template informed consent forms (Arabic and English versions), and any subsequent modifications will be reviewed and approved by the applicable IRB [institutional review board] with respect to scientific content and compliance with applicable research and human subjects' regulations prior to starting the study.

Protocol Amendments

Any modifications to the protocol which may impact on the conduct of the study, potential benefit of the patient or may affect patient safety, including changes of study objectives, study design, patient population, sample sizes, study procedures, or significant administrative aspects will require a formal amendment to the protocol. Such amendments will be reviewed and approved by the IRB prior to implementation in accordance with local regulations.

Administrative changes of the protocol are minor corrections and/or clarifications that have no effect on the way the study is to be conducted will be agreed upon by the principal investigators and documented.

Informed Consent and Participant Rights

Surgical residents will introduce and discuss the trial to patients answering all questions and/or concerns they might have. Patients will then be able to have an informed discussion with the participating consultant. Surgical residents will then obtain written consent from patients willing to participate in the trial. Consent forms are provided for all patients involved in the trial in Arabic or English language.

The informed consent will be a tiered consent. Participants will be given the option to consent for the use of their data in current protocols or for future ancillary research unrelated to the clinical condition under study as well.

All participants will also be given a special follow up card. Any complications, if present, will be treated at the Ain Shams University Hospitals at no additional cost.

Healthcare-Information Security and Privacy

All study-related information will be stored securely at the study site. All participant information will be stored in locked file cabinets in areas with limited access. All data collection, process, and administrative forms will be identified by a coded ID [identification] number only to maintain participant confidentiality. All records that contain names or other personal identifiers, such as locator forms and informed consent forms, will be stored separately from study records identified by code number. All local databases will be secured with password-protected access systems. Forms, lists, logbooks, appointment books, and any other listings that link participant ID numbers to other identifying information will be stored in a separate, locked file in an area with limited access.

The Ain Shams Surgical Research Group will oversee the data storing process. All Principal Investigators will be given access to the cleaned data sets. All data sets will be password protected. To ensure confidentiality, data dispersed to project team members will be blinded of any identifying participant information.

Conflicts of Interest

All principal and team investigators declare no conflict of interest.

Publication Policy

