Involves only skin and subcutaneous tissue of the incision		
AND Patient has at least one of the following:		
a. Purulent drainage from the superficial incision.		
b. Organisms identified from an aseptically-obtained specimen from the superficial incision or subcutaneous tissue by a culture or non-culture based microbiologic testing method, which is performed for purposes of clinical diagnosis or treatment (for example, not Active Surveillance Culture/Testing (ASC/AST)).		
c. Superficial incision that is deliberately opened by a surgeon, physician* or physician designee AND Culture or non-culture based testing of the superficial incision or subcutaneous tissue is not performed AND Patient has at least one of the following signs or symptoms: 
 • Localized pain or tenderness • Localized swelling • Erythema • Heat 		
d. Diagnosis of a superficial incisional SSI by a physician* or physician designee.		
*The term physician for the purpose of application of the NHSN SSI criteria may be interpreted to mean a surgeon, infectious disease physician, emergency physician, other physician on the case, or physician's designee (nurse practitioner or physician's assistant).		
Comments:		
There are two specific types of superficial incisional SSIs:		

 1. Superficial Incisional Primary (SIP) – a superficial incisional SSI that is identified in the primary incision in a patient that has had an operation with one or more incisions (for example, C-section incision or chest incision for CBGB) 2. Superficial Incisional Secondary (SIS) – a superficial incisional SSI that is identified in the secondary incision in a patient that has had an operation with more than one incision (for example, donor site incision for CBGB) 		
Reporting Instructions for Superficial SSI:		
The following do not qualify as criteria for meeting the NHSN definition of superficial SSI:		

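### The call survey omits redness, although redness is meant to trigger a clinic visit, and the local-effects item asks blinded staff to attribute a reaction to povidone-iodine

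*Protocol*

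**What the plan says.** **Commitment.** Secondary outcome 6 (Protocol, Outcomes) is local adverse events of the wash, namely irritation and poor healing. Under Monitoring, known and novel effects of povidone-iodine "will be investigated and recorded until the period of patient follow up is completed", and Participant Timeline sets follow-up at 30 days. Monitoring also defines an adverse event as one with a probable causal relation to the intervention.

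**Schedule.** Participant Timeline gives inpatient observation, one fixed clinic visit after the first week, and then "phone calls made at regular 1-week intervals inquiring about symptoms and signs of SSI based on a questionnaire guided by the CDC definitions". The trigger for a further visit reads: "If a patient displays ≥ 1 symptom listed in the CDC checklist (See appendix 5), he/she will be invited to follow-up" in the outpatient clinic. Data Collection Methods adds "All those who volunteer will be followed up in our clinics", and has the data teams follow patients "over the 30-day follow-up period, according to the methods described above".

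**Tools.** Appendix 5, superficial criterion c, lists pain or tenderness and then "Localized swelling • Erythema • Heat". Appendix 6, item 3-5, is the call survey. Its six questions cover pain or tenderness, swelling, hotness, pus, fever, and an incision opened by a physician. A score of 1/6 or more sends the patient to clinic. At 0/6 the instruction is to repeat the survey at the next interval. Item 3-8 asks about any adverse effect of the povidone-iodine, with boxes for skin reaction, poor healing and other.

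**Blinding.** "The patients and outcome assessors will be blinded".

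**The concern.** Two parts of the follow-up form work against commitments made in the Protocol text. The call survey is narrower than the checklist that is supposed to trigger a visit. The item that records secondary outcome 6 depends on a causal attribution that blinded people cannot make.

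What is at stake is limited: how far the trial can support a statement that the wash was locally well tolerated to day 30. Inpatient observation and the fixed visit cover early effects. The weaker period runs from about the second week, in patients who have gone home and screen negative.

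**Working it through.** The documents give no adverse-event rate, so the check is a comparison of texts. Only the cost of the remedy needs arithmetic.

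**1. Visit trigger against call survey**

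| Local sign | Appendix 5, criterion c | Item 3-5 |
|---|---|---|
| Pain or tenderness | yes | yes |
| Swelling | yes | yes |
| Heat | yes | yes |
| Erythema | yes | no |

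Three of the four local signs reach the calls. In criterion c all four count towards a diagnosis only when the incision has been deliberately opened and not cultured. That does not explain the omission, because swelling and heat stand under the same condition and are both asked about.

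**2. Three patients at home in week 3, with the form followed as written**

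- *Warm, painful wound.* Scores at least 1/6 and goes to clinic.
- *Redness only.* Scores 0/6 and the survey is repeated. Participant Timeline would invite this patient, because erythema is on the checklist.
- *Itchy rash, or a painless wound that has not healed.* Scores 0/6 and is on neither list. Recording depends on the patient volunteering it or on the caller asking something unscripted in order to complete item 3-8.

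Of the six questions, three (pain or tenderness, swelling, hotness) overlap with local irritation. None names redness, itch, rash, blistering or an unhealed wound. Item 3-7 lists wound dehiscence, but only when due to SSI.

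**3. Item 3-8 against Blinding and Monitoring**

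Taken literally, the answer to 3-8 in a control patient is always no, and in a wash patient it requires knowing that the wash was used. A blinded assessor must either guess or ignore the wording. The definition in Monitoring makes the same demand. Items 3-6-1 to 3-6-3 offer a *No* box and 3-8 does not, so a blank may mean no event or not asked. Item 3-7 has the same gap.

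**4. Caller time for added questions**

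Inputs: 760 patients (Sample Size). Calls at about days 14, 21 and 28 make 3 contacts after the visit, or 4 if the form's last interval (28-30 days) is separate. Added time per call is an assumption: 0.5 minute, range 0.25 to 1.

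Hours = patients × contacts × minutes ÷ 60.

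| Minutes per call | 3 contacts (760 × 3 = 2,280) | 4 contacts (760 × 4 = 3,040) |
|---|---|---|
| 0.25 | 9.5 h | 12.7 h |
| 0.5 | 19.0 h | 25.3 h |
| 1 | 38.0 h | 50.7 h |

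These are upper bounds, because the planned 10% loss to follow-up is not deducted.

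**The case against.** The strongest reply is that item 3-5 is an SSI survey and was never the adverse-event tool. Item 3-8 is that tool. It is starred, its boxes match secondary outcome 6, item 3-2 allows completion by phone, item 3-1 tells staff to make contact at every interval, and doctors are responsible for follow-up data to day 30. Its boxes are descriptive and can be ticked without knowing the allocation. Item 3-9 (Clavien-Dindo) would also pick up any deviation from a normal course. Exact call wording often sits in operating instructions.

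Most of this stands. A reader might infer that late local effects go uncollected. The documents do not support that, because 3-8 provides for them. A reader might also infer that redness is outside the follow-up altogether. It is not: it is within the Protocol's own visit trigger and is missing only from the call survey. Nor do the documents support a sizeable under-count. The exposure is a single wash, nothing says that irritation first appears after week 1, and itch, rash and blistering are examples chosen here, not terms from the Protocol.

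One sentence could be read as removing the problem: the statement that all volunteers are followed up in clinics. It names no further scheduled visit, and the teams are referred back to the methods already described, which are one visit, then calls, then clinic if symptomatic.

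Two things remain after the reply. The mismatch between 3-5 and Appendix 5 lies between two tools that the Protocol itself fixes, so it is not detail left to another document. And descriptive boxes do not cure a question, or an adverse-event definition, that calls for attribution under blinding.

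**Conclusion.** The point holds as a minor one. Followed as written, the call survey screens out a patient whose only sign is redness, whom Participant Timeline would bring to clinic. Secondary outcome 6 also rests on an attribution that blinded patients and assessors cannot make. With no scripted question on itch, rash, blistering or a painless unhealed wound, late capture in discharged, screen-negative patients may be incomplete.

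The size cannot be derived and none is claimed. Any difference between arms is probably small, since both arms get the same calls. No effect on the primary outcome is claimed: redness alone does not meet the SSI definition, and Appendix 5 says that cellulitis by itself does not satisfy criterion d. The conclusion assumes that callers work from item 3-5 and its 0/6 rule, and that no further routine visit takes place.

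**What to change.** 1. **Item 3-5:** add redness as a scored question that triggers the clinic visit, so that the survey agrees with Appendix 5.
2. **Every call, both arms, whatever the score:** ask two neutral questions, (a) itching, rash or blistering around the wound and (b) wound edges open or not healed. A yes to either also prompts a clinic visit.
3. **Item 3-8:** reword to *any local wound reaction or poor healing, regardless of cause*, complete it from these answers, and add a *none (asked)* box.
4. **Monitoring:** amend the adverse-event definition so that local wound events are recorded in both arms without a causality judgement. Changing 3-8 alone would leave form and text in conflict.

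**Cost:** slightly longer calls, with the total caller time worked out above; some additional symptom-triggered visits, whose number cannot be estimated from the documents; and one IRB-reviewed amendment. No routine visit or procedure is added. Late events in patients who do not attend would still be patient-reported and not examined.

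### The 345 per group gives about 70% power at two-sided 0.05, not the stated 80%; it fits only a one-sided 5% test that the protocol never declares

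*Protocol*

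**What the plan says.** The Trial Design section describes a "Superiority, parallel group randomized controlled trial, allocation 1:1". The Sample Size section works by "assuming SSI incidence of 10% in control group and 5% in intervention group", "setting power at 80% and α -error at 0.05", and arrives at a "sample size of 345 patient for each group will be needed". It then plans to "enroll an additional 10% of the calculated sample size for each group in anticipation of a loss to follow-up rate of 10" per cent, which gives a total of 760, or 380 per group.

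The protocol does not say whether the alpha is one-sided or two-sided. The Statistical Methods section names no test for the primary outcome, so sidedness cannot be inferred from there either.

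**The concern.** An alpha of 0.05 with no qualifier is normally taken as two-sided, and on that reading 345 per group is too few for the stated power. There are two possibilities, and each leaves a fault in the text:

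- **The final test is two-sided.** The 80% power claim is then false. A null result from a trial with about 70% power, reported as 80%, would be over-read as evidence of no benefit. The Background gives the unclear role of povidone-iodine irrigation as the reason for the trial, so this matters.
- **The final test is one-sided at 5%.** The power claim then holds, but the standard of evidence equals a two-sided 10% test, and the reader is not told.

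Leaving the matter open also allows sidedness to be settled after the data are seen.

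**Working it through.** **Inputs, all from the protocol.** p1 = 0.10 (control), p2 = 0.05 (intervention), power 80%, alpha 0.05 (Sample Size); allocation 1:1 (Trial Design). Hence the difference d = 0.05 and the mean rate is 0.075.

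**Formula (two proportions, pooled variance under the null).**

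n per group = [z_alpha × √(2 × 0.075 × 0.925) + z_beta × √(0.10 × 0.90 + 0.05 × 0.95)]² / d²

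The two square roots are √0.13875 = 0.3725 and √0.1375 = 0.3708, and z_beta = 0.8416.

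**Step 1: reproduce the stated 345.**

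- One-sided 0.05 (z_alpha = 1.6449): (0.6127 + 0.3121)² / 0.0025 = 342.1, so 343. Related one-sided formulas give 341 (unpooled) and 344 (fully pooled). The stated 345 is within rounding of these.
- Two-sided 0.05 (z_alpha = 1.9600): (0.7301 + 0.3121)² / 0.0025 = 434.4, so 435.

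**Step 2: could another two-sided formula give 345?** The alternatives are 424 (arcsine), 432 (unpooled), 436 (fully pooled), 453 (log odds ratio) and 474 (continuity correction). None comes near 345. The gap of about 90 per group is not a matter of rounding or formula.

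**Step 3: power at the numbers planned.** Power = Φ[(d√n − z_alpha × 0.3725) / 0.3708]. For n = 345, two-sided: (0.9287 − 0.7301) / 0.3708 = 0.536, and Φ(0.536) = 0.704.

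| Evaluable per group | Two-sided 0.05 | One-sided 0.05 |
|---|---|---|
| 342 (380 less 10%) | 70.0% | 80.0% |
| 345 (stated need) | 70.4% | 80.3% |
| 380 (no loss at all) | 74.5% | 83.6% |

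Exact binomial enumeration of two-sided power agrees. The uncorrected chi-square test has 71.3% at 345 and 70.9% at 342. Fisher's test is lower, at 66.0% and 65.6%.

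**Step 4: the loss allowance.** 345 × 1.10 = 379.5, so 380 per group and 760 in total. If 10% are lost, 380 × 0.90 = 342 remain, 3 short of 345. To keep 345 after a 10% loss takes 345 / 0.90 = 383.3, so 384 per group and 768 in total. The slip costs 0.3 to 0.4 points of power.

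**Step 5: what the planned size can detect.** With 342 per group and a two-sided 0.05, power is 79.3% for 10% versus 4.5% and 80.2% for 10% versus 4.45%. So 80% power is reached at 10% versus about 4.5%.

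**Step 6: what 80% two-sided power would take.** 435 / 0.90 = 483.3, so 484 per group and 968 in total.

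**The case against.** The best defence is that a one-sided test was intended. The aim is directional (prevention of SSI, in a superiority design), and under a one-sided 5% test 345 is sufficient. On that reading there is no arithmetic error, only an omitted word. The harm clause in the Monitoring section, where the interim look is to "determine if the study should be prematurely terminated in the case of patient harm", concerns safety and does not fix the sidedness of the final efficacy test. The analysis plan, where the test would normally be named, is not at hand.

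Much of this is fair. The 70% figure is conditional on a two-sided test, and the harm clause shows only that a difference in the unfavourable direction is of interest. But a directional aim and the word superiority do not imply a one-sided test, and nothing in the protocol declares one. An analysis plan could not put the Sample Size section right. If it chose a two-sided test, the stated 80% would be false; if one-sided, the section would still need the qualifier.

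The defence is also right that the 342 versus 345 shortfall is trivial. It adds nothing to the weight of the point.

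**Conclusion.** The point holds. Under a two-sided 0.05, the stated design has about 70% power for 10% versus 5%, with a type II error near 30%, and is about 90 evaluable patients per group short of 80%. Even with complete follow-up of all 760 it reaches only 74.5%. The stated figure is right only under an undeclared one-sided 5% test.

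This rests on the protocol's own rates, equal allocation and the standard normal approximation, which exact enumeration of the chi-square test confirms to within about one point. Fisher's test would make the shortfall larger. The text must be corrected, because the main design claim does not follow from its stated inputs as they are ordinarily read.

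**What to change.** Keep 760 patients and rewrite the Sample Size paragraph along these lines: *Two-sided alpha 0.05. With 760 patients enrolled and 10% lost to follow-up, 342 evaluable patients per group give about 70% power to detect SSI rates of 10% versus 5%, or 80% power for 10% versus about 4.5%.* Stating 342 evaluable also settles the loss arithmetic.

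If a one-sided 5% test was truly intended, say so in both Sample Size and Statistical Methods, and report the result as one-sided. In that case 342 evaluable still gives 80.0% power. Enrolling 384 per group (8 more patients in total) is needed only if the sponsor wishes to keep the figure of 345 exactly.

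The cost is one paragraph and a less favourable stated power, with no extra patients. A sponsor who wants a genuine 80% two-sided power for 10% versus 5% would need 968 patients, 208 more than planned. That is the sponsor's choice and is not required to make the document correct.
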